6.4 Concomitant medications

Concomitant medications will be recorded at screening and at every visit during the treatment phase of the study in the case report form (CRF) in the concomitant therapy section.

6.4.1 Prohibited Concomitant Medications

Medications or vaccinations specifically prohibited in the exclusion criteria and described below are not allowed during the ongoing trial. If there is a clinical indication for these or other medications or vaccinations to be used during the trial, then the patient should discontinue trial therapy. The investigator should discuss any questions regarding this with the CI (or delegate). Please refer to the corresponding SmPC for further recommendations on co-administration.

The final decision on any supportive therapy or vaccination rests with the investigator and/or the patient's primary physician. However, the decision to continue the patient on trial therapy or vaccination schedule requires the mutual agreement of the Investigator, and the patient.

Patients are prohibited from receiving the following therapies during the Screening and Treatment Phase of this trial:

- Anti-cancer systemic chemotherapy or biological therapy
- Immunotherapy not specified in this protocol
- Chemoradiotherapy not specified in this protocol
- Investigational agents other than pembrolizumab
- Radiation therapy not specified in the protocol, Live vaccines within 30 days prior to the first dose of trial treatment and while participating in the trial. Examples of live vaccines include, but are not limited to, the following: measles, mumps, rubella, chicken pox, yellow fever, rabies, BCG, and typhoid (oral) vaccine. Seasonal influenza vaccines for injection are generally killed virus vaccines and are allowed; however intranasal influenza vaccines (e.g. Flu-Mist®) are live attenuated vaccines, and are not allowed.
- Glucocorticoids for any purpose other than to modulate symptoms from an event of clinical interest of suspected immunologic etiology or to manage nausea and vomiting during cisplatin treatment. The use of physiologic doses of corticosteroids may be approved after consultation with the Sponsor.

Patient's may receive other medications that the investigator deems to be medically necessary. The Exclusion Criteria describes other medications which are prohibited in this trial. There are no prohibited therapies during the Post-Treatment Follow-up Phase.

6.4.2 Acceptable Concomitant Medications

All treatments that the investigator considers necessary for a patient's welfare may be administered at the discretion of the investigator in keeping with the community standards of medical care. All concomitant medication will be recorded on the case report form (CRF) including all prescription, over-the-counter (OTC), herbal supplements, and IV medications and fluids. If changes occur during the trial period, documentation of drug dosage, frequency, route, and date may also be included on the CRF.

All concomitant medications received within 28 days before the first dose of trial treatment and 30 days after the last dose of trial treatment or initiation of other anti-cancer therapies should be recorded. Concomitant medications administered after 30 days after the last dose of trial treatment should only be recorded for SAEs and overdose and liver toxicity ECIs as defined in Section 7.

6.5 Rescue Medications & Supportive Care

6.5.1 Supportive Care Guidelines

Patients should receive appropriate supportive care measures as deemed necessary by the treating investigator including but not limited to the items outlined below:

6.5.1.1 Diarrhoea:

Patients should be carefully monitored for signs and symptoms of:

- Enterocolitis (diarrhoea, abdominal pain, blood or mucus in stool, with or without fever)
- Bowel perforation (peritoneal signs and ileus).

In symptomatic patients, infectious etiologies should be ruled out, and if symptoms are persistent and/or severe, endoscopic evaluation should be considered.

- In patients with severe enterocolitis (Grade 3):
 - Pembrolizumab will be **permanently discontinued** and treatment with systemic corticosteroids should be initiated at a dose of 1 to 2 mg/kg/day of prednisone or equivalent. When symptoms improve to Grade 1 or less, corticosteroid taper should be started and continued over at least 1 month.
- In patients with moderate enterocolitis (Grade 2):
 - Pembrolizumab should be **withheld** and anti-diarrhoeal treatment should be started. If symptoms are persistent for more than one week, systemic corticosteroids should be initiated (e.g., 0.5 mg/kg/day of prednisone or equivalent). When symptoms improve to Grade 1 or

less, corticosteroid taper should be started and continued over at least 1 month. Guidelines for continuing treatment with pembrolizumab can be found in Appendix 5.

All patients who experience diarrhoea should be advised to drink liberal quantities of clear fluids. If sufficient oral fluid intake is not feasible, fluid and electrolytes should be substituted via IV infusion.

6.5.1.2 Nausea/vomiting:

Nausea and vomiting should be treated aggressively, and consideration should be given in subsequent cycles to the administration of prophylactic antiemetic therapy according to standard institutional practice. Patients should be strongly encouraged to maintain liberal oral fluid intake.

6.5.1.3 Anti-infectives:

Patients with a documented infectious complication should receive oral or IV antibiotics or other anti-infective agents as considered appropriate by the treating investigator for a given infectious condition, according to standard institutional practice.

6.5.1.4 Immune-related adverse events:

Please see Section 6.6 below regarding diagnosis and management of adverse experiences of a potential immunologic etiology.

6.5.1.5 Management of Infusion Reactions:

Acute infusion reactions (which can include cytokine release syndrome, angioedema, or anaphylaxis) are different from allergic/hypersensitive reactions, although some of the manifestations are common to both AEs. Signs and symptoms usually develop during or shortly after drug infusion and generally resolve completely within 24 hours of completion of infusion. Signs/symptoms may include: Allergic reaction/hypersensitivity (including drug fever); Arthralgia (joint pain); Bronchospasm; Cough; Dizziness; Dyspnea (shortness of breath); Fatigue (asthenia, lethargy, malaise); Headache; Hypertension; Hypotension; Myalgia (muscle pain); Nausea; Pruritus/itching; Rash/desquamation; Rigors/chills; Sweating (diaphoresis); Tachycardia; Tumour pain (onset or exacerbation of tumour pain due to treatment); Urticaria (hives, welts, wheals); Vomiting.

The table below shows treatment guidelines for patients who experience an infusion reaction associated with administration of pembrolizumab.

NCI CTCAE Grade	Treatment	Premedication at subsequent dosing
Grade 1 Mild reaction; infusion interruption not indicated; intervention not indicated	Increase monitoring of vital signs as medically indicated until the patient is deemed medically stable in the opinion of the investigator.	None
Grade 2 Requires infusion interruption but responds promptly to symptomatic treatment (e.g., antihistamines, NSAIDS,	Stop Infusion and monitor symptoms. Additional appropriate medical therapy may include but is not limited to: IV fluids	Patient may be pre-medicated 1.5h (\pm 30 minutes) prior to infusion of pembrolizumab with:

NCI CTCAE Grade	Treatment	Pre-medication at subsequent dosing
narcotics, IV fluids); prophylactic medications indicated for < =24 hrs	Antihistamines NSAIDS Acetaminophen Narcotics Increase monitoring of vital signs as medically indicated until the patient is deemed medically stable in the opinion of the investigator. If symptoms resolve within one hour of stopping drug infusion, the infusion may be restarted at 50% of the original infusion rate (e.g. from 100 mL/hr to 50 mL/hr). Otherwise dosing will be held until symptoms resolve and the patient should be pre-medicated for the next scheduled dose. Patients who develop Grade 2 toxicity despite adequate pre-medication should be permanently discontinued from further trial treatment administration.	Diphenhydramine 50 mg po (or equivalent dose of antihistamine). Acetaminophen 500-1000 mg po (or equivalent dose of antipyretic).
Grades 3 or 4 Grade 3: Prolonged (i.e., not rapidly responsive to symptomatic medication and/or brief interruption of infusion); recurrence of symptoms following initial improvement; hospitalization indicated for other clinical sequelae (e.g., renal impairment, pulmonary infiltrates) Grade 4: Life-threatening; pressor or ventilatory support indicated	Stop Infusion. Additional appropriate medical therapy may include but is not limited to: IV fluids Antihistamines NSAIDS Acetaminophen Narcotics Oxygen Pressors Corticosteroids Epinephrine Increase monitoring of vital signs as medically indicated until the patient is deemed medically stable in the opinion of the investigator. Hospitalization may be indicated. Patient is permanently discontinued from further trial treatment administration.	No subsequent dosing
Appropriate resuscitation equipment should be available in the room and a physician readily available during the period of drug administration. For Further information, please refer to the Common Terminology Criteria for Adverse Events v4.0 (CTCAE) at http://ctep.cancer.gov		

Table 11: Infusion Reaction Treatment Guidelines

6.6 Supportive Care Guidelines for Immune-related Adverse Events (irAE) and Immune-related Events of Clinical Interest (irECI)

Immune-related Adverse events (IrAEs) may be defined as an adverse event of unknown etiology, associated with drug exposure and is consistent with an immune phenomenon. irAEs may be predicted based on the nature of the pembrolizumab compound, its mechanism of action, and reported experience with immunotherapies that have a similar mechanism of action. Special attention should be paid to AEs that may be

suggestive of potential irAEs. An irAE can occur shortly after the first dose or several months after the last dose of treatment.

If an irAE is suspected, efforts should be made to rule out cancer, infectious, metabolic, toxin or other etiologic causes prior to labelling an adverse event as an irAE.

Recommendations to managing irAEs not detailed elsewhere in the protocol are detailed in the below table.

irAE	Withhold/Discontinue pembrolizumab?	Supportive Care
Grade 1	No action	Provide symptomatic treatment
Grade 2	May withhold pembrolizumab	Consider systemic corticosteroids in addition to appropriate symptomatic treatment. Based on limited data from clinical studies in subjects whose immune-related adverse reactions could not be controlled with corticosteroid use, administration of other systemic immunosuppressants can be considered.
Grade 3 and Grade 4	Withhold pembrolizumab Discontinue if unable to reduce corticosteroid dose to < 10 mg per day prednisone equivalent within 12 weeks of toxicity	Systemic corticosteroids are indicated in addition to appropriate symptomatic treatment. May utilize 1 to 2 mg/kg prednisone or equivalent per day. Steroid taper should be considered once symptoms improve to Grade 1 or less and tapered over at least 4 weeks. Based on limited data from clinical studies in subjects whose immune-related adverse reactions could not be controlled with corticosteroid use, administration of other systemic immunosuppressants can be considered.

Table 12: General Approach to Handling irAEs

Details for managing specific irAEs are summarised below:

Immune-mediated pneumonitis

Monitor patients for signs and symptoms of pneumonitis. If pneumonitis is suspected, evaluate with radiographic imaging. Exclude other causes of pneumonitis, and manage treatment in accordance with the guidelines above. Administer corticosteroids, withhold pembrolizumab for moderate (Grade 2) pneumonitis, and permanently discontinue pembrolizumab for severe (Grade 3) or life-threatening (Grade 4) pneumonitis.

For Grade 2 pneumonitis that improves to ≤ Grade 1 within 12 weeks, the following rules should apply:

- First episode of pneumonitis
 - May increase dosing interval by one week in subsequent cycles
- Second episode of pneumonitis – permanently discontinue pembrolizumab if upon re-challenge patient develops pneumonitis ≥ Grade 2

Immune-mediated colitis

Monitor patients for signs and symptoms of colitis. Exclude other causes of colitis, and manage treatment in accordance with the guidelines above. Administer corticosteroids, withhold pembrolizumab for moderate (Grade 2) or severe (Grade 3) colitis, and permanently discontinue pembrolizumab for life-threatening (Grade 4) colitis.

Immune-mediated hepatitis

Monitor patients for changes in liver function (at the start of treatment, periodically during treatment and as indicated based on clinical evaluation) and symptoms of hepatitis. Exclude other causes of hepatitis, and manage treatment in accordance with the guidelines above. Administer corticosteroids and, based on severity of liver enzyme elevations, withhold or discontinue pembrolizumab.

Immune-mediated nephritis

Monitor patients for changes in renal function. Exclude other causes of nephritis, and manage treatment in accordance with the guidelines above. Administer corticosteroids, withhold pembrolizumab for moderate (Grade 2), and permanently discontinue pembrolizumab for severe (Grade 3) or life-threatening (Grade 4) nephritis.

Immune-mediated endocrinopathies

Monitor patients for signs and symptoms of hypophysitis (including hypopituitarism and secondary adrenal insufficiency). Exclude other causes of hypophysitis, and manage treatment in accordance with the guidelines above. Administer corticosteroids, withhold pembrolizumab for moderate (Grade 2), withhold or discontinue pembrolizumab for severe (Grade 3) and for life-threatening (Grade 4) hypophysitis.

Monitor patients for hyperglycemia or other signs and symptoms of type 1 diabetes. Administer insulin for type 1 diabetes, and withhold pembrolizumab in cases of severe hyperglycemia until metabolic control is achieved.

Thyroid disorders have been reported in patients receiving pembrolizumab and can occur at any time during treatment; therefore, monitor patients for changes in thyroid function (at the start of treatment, periodically during treatment and as indicated based on clinical evaluation) and clinical signs and symptoms of thyroid disorders. Administer corticosteroids, withhold pembrolizumab for severe (Grade 3) hyperthyroidism, and permanently discontinue pembrolizumab for life-threatening (Grade 4) hyperthyroidism. Treat symptoms of hyperthyroidism as appropriate. Isolated hypothyroidism may be managed with replacement therapy without treatment interruption and without corticosteroids. For patients with severe (Grade 3) or life-threatening (Grade 4) endocrinopathy that resolved and is controlled with hormone replacement, continuation of pembrolizumab may be considered.

Other immune-mediated adverse events

Across clinical studies with pembrolizumab in approximately 5000 patients, the following additional clinically significant, immune-mediated adverse reactions were reported in less than 1% of patients: uveitis, [Guillain-Barre syndrome](#), and severe skin reactions.

In addition a set of irAEs have also been classified as immune-related events of clinical interest (irECI) a full list of these can be found in Appendix 5. Patients with symptomatic irECIs should immediately stop receiving pembrolizumab and be evaluated to rule out non treatment related causes of the event. Overdose and liver toxicity irECIs irrespective of relationship to the study drug should be reported within 24 hours of the investigator being aware to the Sponsor who will in turn notify MSD. If the irECI is determined to be associated please refer to Appendix 5 for the recommendations on the management of these irECIs. If the event is not considered to be associated with the study drug the physician should exercise individual clinical judgment on the event management based on the patient. Any additional questions of the collection or information on management of irECIs should be directed to the Sponsor.

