7.6 Events of Clinical Interest

7.6.1 Definitions of Evidence of Clinical Interest (ECI)

Selected non-serious and serious adverse events can also be classified as Events of Clinical Interest (ECI) and overdose and liver toxicity ECIs must be reported as described in section 7.5.2.

Events of clinical interest for this trial include:

1. An overdose of pembrolizumab, as defined in Section 7.7 that is not associated with clinical symptoms or abnormal laboratory results.
2. A Drug induced liver injury (DILI) defined as elevated AST or ALT lab value that is greater than or equal to 3X the upper limit of normal

AND / OR

An elevated total bilirubin lab value that is greater than or equal to 2X the upper limit of normal

AND / OR

An alkaline phosphatase lab value that is less than 2X the upper limit of normal, as determined by way of protocol-specified laboratory testing or unscheduled laboratory testing.

3. Any AEs identified in the below table 13 can be classified as immune-related events of clinical interest. A detailed narrative of overdose and liver toxicity ECIs should be reported as described in section 7.5.2:

Pneumonitis - (classified as ECI if \geq Grade 2)

Acute interstitial Pneumonitis	Interstitial Lung Disease	Pneumonitis		
Colitis - (classified as ECI if \geq Grade 2 or any grade resulting in dose modification or use of systemic steroids to treat the AE)				
Intestinal Obstruction	Colitis	Colitis microscopic		
Enterocolitis	Enterocolitis hemorrhagic	Gastrointestinal perforation		
Necrotising colitis	Diarrhoea			
Endocrine - (classified as ECI if \geq Grade 3 or \geq Grade 2 and resulting in dose modification or use of systemic steroids to treat the AE)				
Adrenal Insufficiency	Hyperthyroidism	Hypophysitis		
Hypopituitarism	Hypothyroidism	Thyroid disorder		
Thyroiditis	Hyperglycemia, if \geq Grade 3 and associated with ketosis or metabolic acidosis (DKA)			
Endocrine (classified as ECI)				
Type 1 diabetes mellitus (if new onset)				
Hematologic - (classified as ECI if \geq Grade 3 or any grade resulting in dose modification or use of systemic steroids to treat the AE)				
Autoimmune haemolytic anaemia	Aplastic anaemia	Thrombotic thrombocytopenic purpura		
Idiopathic thrombocytopenia purpura	Disseminated intravascular coagulation	Haemolytic uraemic syndrome		
Any grade 4 anaemia regardless of underlying mechanism				

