12.5 APPENDIX 5: Identification, evaluation and management of ECIs

ECI	Grade	Action to be taken	Supportive Care
Pneumonitis –	Grade 1 (Asymptomatic)	• No action	• Intervention not indicated
	Grade 2	• Withhold pembrolizumab, may restart if Grade 1 or	• 1-2mg/kg/day prednisone or equivalent. • Symptoms grade 1 or less, initiate steroid

		
 resolved within 12 weeks Consider bronchoscopy and biopsy/BAL, ID Consult and frequent chest x-ray for monitoring. Conduct in person evaluation twice a week 	
 taper for no less than 4 weeks. Permanently discontinue pembrolizumab if dose cannot be reduced to 10mg prednisone or less or equivalent per day within 12 weeks.
	Grade 3 and 4	
 Discontinue pembrolizumab Hospitalize patient Bronchoscopy with biopsy and/or BAL is recommended. 	
 methylprednisolone 125mg IV. Symptoms grade 1 or less initiate steroid taper for no less than 4 weeks 
 Prednisone 1 to 2 mg/kg/day or dexamethasone 4mg every 4 hours If IV steroids do not reduce initial symptoms within 48-72 hours treat with additional anti-inflammatory measures. At symptom relief discontinue anti-inflammatory and start steroid taper over 45-60 days. If symptoms worsen during this period refer to section 6 and 7.

 1st episode - May increase dosing interval by one week in subsequent cycles 2nd episode of - Pneumonitis Permanently discontinue pembrolizumab if upon re-challenge patient develops Pneumonitis ≥ Grade 2 			
Colitis	Grade 1 (Asymptomatic)	
 No action 	
 Intervention not indicated
	Grade 2 (For grade 2 diarrhoea that persists > 3 days)	
 Withhold pembrolizumab, may restart if Grade 1 or resolved within 12 weeks Symptomatic treatment 
 Consider GI consult & endoscopy to rule out colitis 	
 Prednisone 1-2mg/kg/day or equivalent Symptoms grade 1 or less, initiate steroid taper for no less than 4 weeks. Permanently discontinue pembrolizumab if dose cannot be reduced to 10mg or less of prednisone or equivalent per days within 12 weeks. If symptoms worsen or persist >1 week treat as grade 3.

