	Grade 3	
 Withhold pembrolizumab Rule out bowel perforation Recommend gastroenterologist consult & biopsy with endoscopy 	
 methylprednisolone 125mg IV followed by prednisone 1 to 2 mg/kg/day or dexamethasone 4mg every 4 hours. Symptoms grade 1 or less initiate steroid taper for no less than 4 weeks. Taper 6-8 weeks in patients with diffuse or severe ulceration and/or bleeding If IV steroids do not reduce initial symptoms within 48-72 hours treat with additional anti-inflammatory measures. At symptom relief discontinue anti-inflammatory and initiate steroid taper over 45-60 days. If symptoms worsen during this period refer to Section 6 and 7.
	Grade 4	
 Discontinue pembrolizumab 	
 Manage as per grade 3
Endocrine –	Grade 1	
 No action 	
 Intervention not indicated

Hypo and hyperthyroidism	(Asymptomatic)		
	Grade 2 Hyperthyroidism and Grade 2- 4 Hypothyroidism	
 Monitor thyroid function until returned to baseline. Consider consultation with endocrinologist. Pembrolizumab can continue while on this treatment. 	
 Thyroid hormone and/or steroid replacement therapy. Hyper – non-selective beta blockers for initial therapy Hypo – thyroid hormone replacement therapy as per standard of care.
	Grade 3 Hyperthyroidism	
 Withhold pembrolizumab, may restart if Grade 1 or resolved within 12 weeks Rule out infection and sepsis. 	
 IV methylprednisolone 1-2mg/kg followed by prednisone 1-2mg/kg per day. Symptoms grade 1 or less initiate steroid taper for no less than 4 weeks. Replacement of appropriate hormones may be required. Permanently discontinue pembrolizumab if dose cannot be reduced to prednisone 10mg or less or equivalent per day within 12 weeks.
	Grade 4 Hyperthyroidism	
 Discontinue pembrolizumab 	
 Manage as per grade 3
Endocrine – Hypophysitis or other symptomatic endocrinopathy	Grade 1 (Asymptomatic)	
 No action 	
 Intervention not indicated

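### Grade 2 enterocolitis/colitis has inconsistent steroid guidance in sections 6.5.1.1, 6.6 and Appendix 5, with stated doses that differ 2- to 4-fold and no rule on which text governs

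*Combined protocol and SAP*

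**What the plan says.** Three places in the combined protocol and SAP address steroids for Grade 2 bowel inflammation.

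- **Section 6.5.1.1 (Diarrhoea), moderate enterocolitis.** Pembrolizumab is withheld "and anti-diarrhoeal treatment should be started". Steroids come later: "If symptoms are persistent for more than one week, systemic corticosteroids should be initiated (e.g., 0.5 mg/kg/day of prednisone or equivalent". No further escalation is described within Grade 2. The paragraph closes with "Guidelines for continuing treatment with pembrolizumab can be found in Appendix 5".
- **Section 6.6, immune-mediated colitis.** Corticosteroids are to be given and pembrolizumab held at Grade 2 or Grade 3. No dose and no waiting period are stated. The paragraph also defers, in general terms, to guidelines above it.
- **Section 12.5 (Appendix 5), colitis, Grade 2 row.** The grade cell carries the qualifier "For grade 2 diarrhoea that persists > 3 days". The supportive-care cell gives "Prednisone 1-2mg/kg/day or equivalent" and ends with "If symptoms worsen or persist >1 week treat as grade 3". The Grade 3 row to which this leads reads "methylprednisolone 125mg IV followed by prednisone 1 to 2 mg/kg/day or dexamethasone 4mg every 4 hours".

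**The concern.** A clinician with a Grade 2 patient who consults one section gets a different steroid instruction from a colleague who consults another. They differ on the dose, on whether a week of anti-diarrhoeal treatment comes first, and on whether a persisting Grade 2 case moves to a Grade 3 pathway.

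Colitis is an immune toxicity that the protocol itself anticipates for the study drug, so this is a safety matter first. It is also a matter of consistent conduct. The primary endpoint is safety and tolerability, and escalation decisions are taken on cohorts of three to six patients per HPV group. It is undesirable for management of an anticipated immune toxicity to depend on which page was read. The documents give no expected frequency of Grade 2 colitis under this combination, so the number of patients affected cannot be estimated.

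**Working it through.** The plan states no figure to reproduce. The check compares the texts and takes one ratio.

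**Side by side, Grade 2**

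| Item | 6.5.1.1 | 6.6 (colitis) | Appendix 5 (colitis) |
|---|---|---|---|
| Pembrolizumab | Withhold | Withhold | Withhold |
| First measure | Anti-diarrhoeal treatment | Corticosteroids | Symptomatic treatment and prednisone |
| Steroid start | After more than one week of symptoms | No waiting period stated | Row qualified by diarrhoea beyond 3 days; no separate start rule |
| Prednisone dose | 0.5 mg/kg/day, as an example | Not stated | 1 to 2 mg/kg/day |
| Escalation within Grade 2 | None | None | To Grade 3 on worsening or after more than one week |
| Taper | At least 1 month | Not stated | At least 4 weeks |

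The texts agree on withholding pembrolizumab. Where a taper is given, its length agrees in substance. The disagreement is confined to steroid start, dose and escalation.

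**Dose ratio** (Appendix 5 dose divided by 6.5.1.1 dose)
- Lower end: 1 / 0.5 = 2.
- Upper end: 2 / 0.5 = 4.

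For illustration, with assumed body weights of 50 to 90 kg:
- 6.5.1.1: 0.5 × 50 = 25 to 0.5 × 90 = 45 mg/day.
- Appendix 5 at 1 mg/kg: 50 to 90 mg/day.
- Appendix 5 at 2 mg/kg: 100 to 180 mg/day.

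**The one-week period in Appendix 5.** The text does not say where it starts, so both readings are shown.
- *From symptom onset.* Escalation falls after more than 7 days of symptoms, when 6.5.1.1 would first start a steroid. The contrast is then 0.5 mg/kg/day against the Grade 3 regimen.
- *From steroid start.* If steroids begin as soon as the row applies (an assumption), escalation falls after more than 3 + 7 = 10 days of symptoms. Between day 7 and day 10 the contrast is 0.5 against 1 to 2 mg/kg/day. Beyond day 10 it is 0.5 mg/kg/day against the Grade 3 regimen.

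The sections differ under either reading. Only the timing and size of the difference change.

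**Do the texts cover the same patient?**
1. Table 13 (section 7.6.1) lists enterocolitis and diarrhoea in its colitis group, "classified as ECI if \geq Grade 2 or any grade resulting in dose modification or use of systemic steroids to treat the AE". A Grade 2 event therefore qualifies by grade.
2. Section 6.6 refers immune-related ECIs judged to be associated with study drug to Appendix 5 for management.
3. Section 6.5.1.1 addresses Grade 2 enterocolitis directly, without limiting itself to non-immune causes.

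A drug-associated Grade 2 enterocolitis thus falls under 6.5.1.1, 6.6 and Appendix 5 together. No sentence says which prevails.

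**The case against.** The strongest defence is that the sections can be read together. Section 6.5.1.1 would cover ordinary diarrhoea. Section 6.5.1.4 sends potentially immune events to 6.6, and 6.6 sends drug-associated ones to Appendix 5. The 0.5 mg/kg/day is only an example, section 6.5.1 leaves supportive care to the treating investigator, and 6.6 calls the Appendix 5 content recommendations. The colitis paragraph in 6.6 also defers to guidelines above it, which might be taken to include 6.5.1.1.

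Part of this stands. There is some routing towards Appendix 5, and discretion softens the conflict. It does not remove it:
- The example dose lies outside the Appendix 5 range, and being an example does not qualify the one-week wait.
- The split between ordinary and immune diarrhoea is hard to sustain. Section 6.4.1 restricts glucocorticoids during treatment essentially to suspected immune events and cisplatin-related nausea and vomiting, with physiologic doses subject to consultation. The steroid step in 6.5.1.1 therefore reads as treatment of a suspected immune event.
- The reference in 6.6 to guidelines above does not say which ones. Routing of this kind is not a statement of precedence.

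Some stronger readings are tempting but not supported:
- *Appendix 5 has already escalated when 6.5.1.1 first gives a steroid.* This holds only if both one-week periods run from symptom onset. The Appendix 5 sentence follows the steroid and taper entries and can equally mean persistence despite steroids.
- *Steroids start after 3 days in one text and after 7 in the other.* The 3-day phrase qualifies the Appendix 5 row; it is not worded as a steroid trigger.
- *Section 6.5.1.1 itself imports the Appendix 5 steroid rules.* Its cross-reference concerns only continuing pembrolizumab. The overlap rests on Table 13 and section 6.6.

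**Conclusion.** The inconsistency is real and is one of wording. For the same drug-associated Grade 2 event, the stated prednisone doses differ 2- to 4-fold. One text waits more than a week before steroids, another states no wait, and only Appendix 5 has an escalation step, whose starting point it leaves open. The conclusion rests on reading Table 13 and the referral in section 6.6 as bringing Grade 2 enterocolitis under Appendix 5, and on the absence of a precedence rule.

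Two consequences that a reader might infer do not follow. The choice of steroid regimen does not alter ECI classification at Grade 2, because Table 13 already captures the event by grade. Nor do the documents show that either regimen would alter who fails the rule requiring reduction to 10 mg of prednisone within 12 weeks: the taper lengths agree, and nothing links starting dose to failure of that rule. The case for correction is patient safety and uniform management, not a demonstrated effect on an endpoint. It should be corrected. No view is taken here on which instruction is clinically right.

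**What to change.** Reconcile section 6.5.1.1, the immune-mediated colitis paragraph of section 6.6 and the Appendix 5 colitis rows for Grades 2 and 3. Keep one instruction in one place and have the other sections refer to it without restating doses or timing. That instruction should state:

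- when systemic steroids start, and whether the 3-day phrase is a condition for steroids or only for entering the row;
- the dose;
- whether and when a Grade 2 case is escalated, and whether the one-week period runs from symptom onset or from steroid start.

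Because escalation leads to Grade 3, the text should also name the Grade 3 entry it means. Section 6.5.1.1 and Appendix 5 differ on pembrolizumab at that grade (permanent discontinuation against withholding), which needs reconciling in the same edit.

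The clinical content is for the sponsor and investigators to decide. The cost is a change of protocol wording, with no effect on sample size, visits or analysis.
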